## Protocol for NCT04497727

1. **Project Title:** Gut Inflammation and Gut-Gut Microbiome Interactions in the Pathogenesis of Hypertension.
2. **Investigators:** Drs. [name], [name], [name], [name] and [name].
3. **Abstract:** Dysbiosis of the gut microbiome has been associated with a variety of disorders and disease conditions ranging from mental health diseases to obesity. One such disease is hypertension. The initial point of contact between the gut microbiome and the host is their gut epithelium. The gut epithelium and the gut microbiota have evolved together to exist in balance during health. The epithelium has barrier, immune and metabolic functions that support and contain the microbiota. The microbiota in turn makes products that support the health of the gut epithelium, such as short chain fatty acids. There is emerging evidence to suggest that the gut itself, as well as the gut microbiome, is disturbed during hypertension. Little is known about this from animal models of hypertension except in studies by our group, and even less is known about the health of the gut in people with hypertension. We aim to examine the gut epithelium of the colon from colonoscopy biopsies, and we will derive gut organoids from this tissue. We will test the hypothesis that gut epithelium is distinct in terms of basic growth and differentiation and gene expression, in people with hypertension compared to those without cardiovascular disease (CVD) and normal blood pressure (e.g. reference subjects)
4. **Background:** It is estimated that almost half of the adults in the United States have high blood pressure, a leading modifiable risk factor for CVD, stroke and dementia. Approximately 20% of these people are termed treatment-resistant hypertensives because they do not achieve goal blood pressures even taking three or more antihypertensive medications of different classes .  
The gut and its microbiome have been shown to be associated with hypertension in both animal models and patients. The gut microbiome is distinct in people and animals with hypertension from those with normal blood pressure. Both the bacterial populations of the gut microbiome and the functions of those populations differ. Most strikingly, the transfer of fecal matter from hypertensive people or animals to animals with normal blood pressure increases their blood pressure. In animal models of hypertension, gut pathology such as decreased villus length and goblet cell number and increased fibrosis and muscularis layer are also observed. Additionally, the gut barrier has reduced strength in hypertensive animals allowing large molecules normally retained in the gut to enter (“leak”) into the blood circulation. In humans with hypertension there is also evidence of gut leakiness as there are increased markers of barrier dysfunction and substances normally well contained behind the gut barrier appear in the circulation. Furthermore, there are more immune cells with surface markers targeting them to the gut in the circulation of hypertensive subjects, another sign that there is a potential problem in the gut. We also have unpublished data in experimental models that gut epithelial cells express different proteins when the animal is hypertensive. Altogether, this suggests that the gut and its microbiome may be a novel target for blood pressure control.  
Gut pathology has not been explored in human hypertension, except by the above-mentioned circulating markers. This has prompted us to hypothesize that the interaction

between the gut and its microbiota is faulty in hypertension, particularly in the light of observations of a good balance between the two in health.

We propose to investigate these interactions in human gut by utilizing colonoscopy biopsies for two main purposes. Firstly, to examine the gene expression profile of the gut epithelium from individuals with and without hypertension. Secondly, we will use the crypts of the gut to culture gut organoids from the stem cells present in the crypts. These are three dimensional cultures that grow and differentiate to form an organ that is structurally similar to the gut. They have a lumen, a polarized epithelium, good barrier function and contain all of the cell types in the correct proportions that are found in the gut epithelium *in vivo*. We will use these to test whether there is a fundamental difference in the epithelium of the gut in hypertension compared to normotension. We will also test gut organoid growth and differentiation in direct comparison to those from normotensive individuals grown under identical culture conditions. In these, we hypothesize that there will be no difference between those from people with hypertension compared to those without hypertension in terms of cellular composition and gene expression patterns.

## 5. Specific Aims:

We will compare basic properties of gut epithelia of hypertensive and normotensive reference subjects. We will determine if there are fundamental differences in the gut epithelium in hypertension compared to normotension. We propose the following aims:

**Aim 1:** To determine if gene expression patterns are distinct in gut epithelium derived from hypertensive compared to normotensive reference individuals.

**Aim 2:** To determine if gut organoids prepared from gut biopsies have different growth rates and patterns, including the proportions of cell populations in the organoids, when derived from hypertensive versus normotensive reference subjects.

## 6. Research Plan:

These studies will include a controlled sampling of human hypertension (n=60, 30 hypertensive subjects and 30 normotensive reference subjects, equal numbers of males and females) recruited at UF.

**Aim 1:** From one part of the biopsy, the gut epithelium will be isolated, and immediately frozen (-80 degrees) until RNA isolation for RNA sequencing and examination of gene expression within the epithelium.

**Aim 2:** The remainder of the biopsy will be immediately (within 30 minutes of collection) used to prepare gut organoid cultures using methods essentially as developed by StemcellTM Technologies. The growth parameters and the proportions of each cell type, for example, enterocyte, Paneth, goblet, enteroendocrine, making up the organoid will be determined by immunohistochemistry or fluorescence activated cell sorting (FACS) analysis.

**Recruitment:** University of Florida (UF) will recruit participants from the UF GI clinic (with and without hypertension) who are scheduled for routine “surveillance” colonoscopy. Most patients undergoing screening colonoscopy have polyps noted (at UF, our adenoma detection rate is around 50%). These folks would have biopsies of other sites (polyps) already, and would get additional biopsies for study. The other 50% without polyps would only have biopsies as part of study. During screening of upcoming “surveillance” colonoscopies potential

participants will be asked by their gastroenterologist about their interest in taking part in this study. If the patient agrees to participate or desires more information about the study, the study coordinators in Cardiology Clinical Trials will contact the patient via phone, email, or an in-person meeting and provide more details and answer any questions. If they wish to take part in the trial, informed consent will be obtained prior to the colonoscopy procedure..

In order to address our hypotheses, colonoscopy biopsies from subjects diagnosed with hypertension as well as a reference group will be collected. After which, a member of [name] or [name] group will immediately transport biopsy samples to [name] lab in the McKnight Brain Institute Building L4-135.

**A. Specific Procedures: Inclusion/exclusion criteria for hypertension participants**

*Inclusion criteria:*

- Ages: 18-80 years old with a weight  $\geq 110$  lbs.
- Diagnosis of hypertension or without hypertension for the reference cohort. 2017 ACC/AHA definition for hypertension (systolic blood pressure  $\geq 130$  mmHg and/or diastolic BP  $\geq 80$  mmHg) will be used.
- Scheduled elective colonoscopy.

*Exclusion criteria:*

- Hypertensive or reference individuals with history of autoimmune disease or other chronic inflammatory conditions.
- Pregnant or have been pregnant in the last six months.
- Antibiotic treatment within two months of study enrollment
- Currently taking a medication(s) (e.g. antibiotic, anti-inflammatory agents, glucocorticoids, other immune modulating medications, antacids or proton pump inhibitor drugs like Prilosec) known to modify gut microbiota or currently taking a medication(s) and stopping the medication(s) to prepare for the colonoscopy then restarting after procedure is completed.
- The use of probiotics
- History of intestinal surgery, inflammatory bowel disease, celiac disease, lactose intolerance, chronic pancreatitis or other malabsorption disorder.
- History of blood transfusion within 4 weeks.
- Subjects who, in the opinion of the investigator, will be uncooperative or unable to comply with study procedures

Subjects will participate until the biopsy procedure is completed.

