**Specific Procedures:**

- Methods/Statistical Analyses: Each study participant will provide, in addition to body weight, BMI, BP, PR, and CVD risk factors, a colonoscopy biopsy.
- Analysis of gene expression in the epithelium of a portion of the biopsy will be examined and gut organoids cultured from the remainder.
- The subjects' medical records will be reviewed and summarized for the study. All collected data will be stored in an encrypted computer data base kept behind UF's firewall. These data will be coded and connected to the biopsy samples by code, not identifiers. Biopsy samples will be processed immediately and portions either frozen for storage or the crypts isolated for gut organoid culture. The experiments will be performed in [name] laboratory in the McKnight Brain Institute and remaining samples stored until the end of the study. Experiments examining gene expression in the colonic epithelium of normotensive and hypertensive rats using the same methodology intended for use here, revealed significant differences between groups with a sample size of n=4 per group. Hence, we expect a sample size of n=60 to provide sufficient power to observe differences in gene expression. Multiple gut organoids can be generated from a single biopsy. This allows mean characteristics for each individuals' organoids to be determined, reducing variability. We have no previous data upon which to base a formal power analysis. However, we believe these culture conditions, the ability to have multiple repetitions of the experiment in each biopsy sample, and 30 subjects per group will be adequate to determine whether there are differences worth pursuing in a larger cohort of hypertensive and normotensive subjects in a future study.

Prepped colonoscopy biopsies: [name], [name], and [name] in the UF GI Division will perform all colonoscopy procedures on subjects (hypertensive or healthy reference subjects) to obtain colon biopsies. All subjects will have up to 4 additional biopsies collected for research. Biopsy and blood samples will be coded as quickly as possible and securely stored with only a subject number assigned for this study.

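### Does section 6.A need a stated rule for which blood pressure reading decides group, and for undiagnosed people at or above 130/80 mmHg?

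*Combined protocol and SAP*

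**What the plan says.** Section 6.A gives one entry criterion for both groups: "Diagnosis of hypertension or without hypertension for the reference cohort. 2017 ACC/AHA definition for hypertension (systolic blood pressure" at or above 130 mmHg and/or diastolic at or above 80 mmHg. Other parts of the protocol describe the groups further.

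- **Reference group.** The abstract (section 3) sets hypertensive people against a comparison group: "compared to those without cardiovascular disease (CVD) and normal blood pressure (e.g. reference subjects". Aim 1 in section 5 studies epithelium "derived from hypertensive compared to normotensive reference individuals". Section 6 plans for "30 hypertensive subjects and 30 normotensive reference subjects".
- **Hypertensive group.** Section 6, under Recruitment, says "colonoscopy biopsies from subjects diagnosed with hypertension as well as a reference group will be collected".
- **Blood pressure data.** The Methods/Statistical Analyses item says "Each study participant will provide, in addition to body weight, BMI, BP, PR, and CVD risk factors, a colonoscopy biopsy". It does not say how or when the pressure is taken.
- **Records.** The Medical Record Abstraction paragraph has history abstracted for every participant and results related to controlled, uncontrolled and treatment-resistant hypertension. The Subject Confidentiality paragraph has the record, including medical history, reviewed to verify eligibility.

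**The concern.** The criterion joins a diagnosis to a numerical cut-off without saying how the two combine. Two questions follow.

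1. Is an undiagnosed person at or above 130/80 enrolled as hypertensive, because the definition is met, or not enrolled, because there is no diagnosis?
2. Which pressure is compared with the cut-off: a charted value, a reading at a meeting, or one on the day of the procedure?

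The second question looks sharper given the contact schedule. Coordinators "will contact the patient via phone, email, or an in-person meeting and provide more details and answer any questions", so an in-person meeting is optional, and "Subjects will participate until the biopsy procedure is completed". A reader could conclude that the only reading available for everyone is one taken after bowel preparation.

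At stake is the exposure itself. Both aims compare hypertensive with normotensive tissue and nothing else. Putting undiagnosed people in the wrong group would probably dilute that comparison, and with 30 per group there is little room for dilution.

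**Working it through.** **Step 1. Who is placed by the text as it stands.** Four kinds of person can present.

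| Diagnosis | Current BP | What the protocol implies | Basis |
|---|---|---|---|
| Yes | Below 130/80 | Hypertensive | Recruitment wording; controlled hypertension is one of the types to be analysed |
| Yes | At or above | Hypertensive | Diagnosis and definition agree |
| No | Below | Reference | Abstract, section 5, section 6 |
| No | At or above | Not reference; hypertensive entry not expressly settled | Abstract, section 5 and section 6 bar the reference group; Recruitment wording points to not enrolling |

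Three of the four are settled. In the fourth, the reference group is ruled out. The natural reading of 6.A is that its second sentence says what a diagnosis of hypertension means, rather than opening a second route of entry. That agrees with the Recruitment wording and leaves the fourth person out of the study.

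**Step 2. Which reading.** The text names none. It does name a source for eligibility, the medical record. The record shows whether there is a diagnosis and may hold earlier pressures. Contacts before the procedure are not shown to be remote either: patients come from the GI clinic, the gastroenterologist raises the study, and consent precedes the colonoscopy. It therefore does not follow that a reading after bowel preparation must decide. The split into controlled and uncontrolled sits under record abstraction, and nothing ties it to the BP in the Methods item.

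**Step 3. How often one reading could mislead near the cut-off.** The protocol gives no BP variability, so this is an illustration. Assume normal within-person, between-day systolic variation with SD 6, 9 or 12 mmHg, and let m be the number of readings on separate days:

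P(wrong side of 130) = 1 − Φ( distance / (SD/√m) )

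Example: distance 5, SD 6, m = 1 gives 1 − Φ(0.833) = 0.202.

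| Usual systolic, distance from 130 | m | SD 6 | SD 9 | SD 12 |
|---|---|---|---|---|
| 5 mmHg | 1 | 0.202 | 0.289 | 0.338 |
| 5 mmHg | 2 | 0.119 | 0.216 | 0.278 |
| 10 mmHg | 1 | 0.048 | 0.133 | 0.202 |
| 10 mmHg | 2 | 0.009 | 0.058 | 0.119 |

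**Step 4. What these figures do and do not show.** They apply only to undiagnosed people near the cut-off, whose number is unknown. They use systolic pressure alone, whereas the criterion is systolic and/or diastolic:

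- For a usual systolic of 135, entry to the reference group also needs a diastolic below 80, so the figure is an upper bound on that error.
- For a usual systolic of 125, a high diastolic can also cross the line, so the figure is a lower bound. If a diagnosis is required, though, this error only costs an enrolment and puts nobody in the wrong group.

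**Step 5. Link to sample size.** The Methods item says there were no earlier data for a formal power analysis. The 30 per group therefore rests on no stated effect size, SD or alpha, and no power figure in the plan is put in doubt.

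**The case for a change.** The strongest case for a change is that the missing reading matters whichever way the criterion is read. If the definition governs, it needs a pressure to be applied to. If the diagnosis governs, reference subjects must still be shown to be normotensive, and the lack of a charted diagnosis does not prove a pressure below 130/80. Charted values, an optional meeting and the procedure day are all compatible with the text and can disagree for one person. One added sentence would cost almost nothing.

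Part of this stands. No section names the deciding pressure, and none says expressly that undiagnosed people at or above the cut-off are not enrolled. Three things limit its weight:

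- Writing out the rule would mostly restate what the other sections already imply.
- Asking the sponsor to name a reading does not show that the one investigators would use anyway is poor. A charted diagnosis with recorded pressures is a sound basis, and the record review is already planned.
- A second separate-day reading reduces the error near the cut-off without removing it: at 5 mmHg the range goes from 20%–34% to 12%–28%.

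Recording antihypertensive use would also add little, since the treatment-resistant category already calls for drug history in the hypertensive group.

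**Conclusion.** No change to the plan follows. The omission is real but is a matter of operating detail. Diagnosed patients are placed in the hypertensive group whatever their current pressure, people at or above 130/80 are kept out of the reference group, and the record is the stated source for eligibility. The residue is confined to undiagnosed people within a few mmHg of the cut-off.

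The only size available is the illustration: at 5 mmHg from 130, a 20% to 34% chance per person of falling on the wrong side with one reading. It rests on an assumed SD of 6 to 12 mmHg, normal variation and systolic pressure alone. The documents do not say how many such people there would be, so no number misclassified, dilution or loss of power can be derived.

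The study's stated purpose is to see whether differences merit a larger cohort. Pressure and abstracted history are collected for every participant, so borderline people can be identified and the way the groups were formed can be reported. The conclusion assumes that staff apply the charted diagnosis and recorded pressures in the same way to both groups, which is the ordinary reading of the text.

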**Specific Procedures:**

- Methods/Statistical Analyses: Each study participant will provide, in addition to body weight, BMI, BP, PR, and CVD risk factors, a colonoscopy biopsy.
- Analysis of gene expression in the epithelium of a portion of the biopsy will be examined and gut organoids cultured from the remainder.
- The subjects' medical records will be reviewed and summarized for the study. All collected data will be stored in an encrypted computer data base kept behind UF's firewall. These data will be coded and connected to the biopsy samples by code, not identifiers. Biopsy samples will be processed immediately and portions either frozen for storage or the crypts isolated for gut organoid culture. The experiments will be performed in [name] laboratory in the McKnight Brain Institute and remaining samples stored until the end of the study. Experiments examining gene expression in the colonic epithelium of normotensive and hypertensive rats using the same methodology intended for use here, revealed significant differences between groups with a sample size of n=4 per group. Hence, we expect a sample size of n=60 to provide sufficient power to observe differences in gene expression. Multiple gut organoids can be generated from a single biopsy. This allows mean characteristics for each individuals' organoids to be determined, reducing variability. We have no previous data upon which to base a formal power analysis. However, we believe these culture conditions, the ability to have multiple repetitions of the experiment in each biopsy sample, and 30 subjects per group will be adequate to determine whether there are differences worth pursuing in a larger cohort of hypertensive and normotensive subjects in a future study.

Prepped colonoscopy biopsies: [name], [name], and [name] in the UF GI Division will perform all colonoscopy procedures on subjects (hypertensive or healthy reference subjects) to obtain colon biopsies. All subjects will have up to 4 additional biopsies collected for research. Biopsy and blood samples will be coded as quickly as possible and securely stored with only a subject number assigned for this study.

**Medical Record Abstraction.** For participants in this study, their pertinent medical history will be abstracted from their records and entered into a RedCap database. These data will be correlated with the research results to determine any relationships or mechanisms in hypertension. We will correlate the research results with the type of hypertension (i.e. controlled, uncontrolled, treatment-resistant).

**Subject Confidentiality.** Clinical information will not be released without written permission of the subject. The site Investigator must assure that the privacy of subjects, including their personal identity and personal medical information, will be maintained at all times. UF site has additional privacy obligations to study subjects under the Health Insurance Portability and Accountability Act (HIPAA). After a subject has signed an informed consent form, the coordinator will review the signed informed consent(s) and the PI will review that portion of the subject's medical record that is directly related to the study including electronic medical records. This shall include all study relevant documentation including subject medical history to verify eligibility, laboratory test result reports, admission/discharge summaries for hospital admissions occurring while the subject is in the study, and autopsy reports for deaths occurring during the study (when available). All study files will be kept on site in locked drawers. The only personnel with access to this data are the PI and study staff. All data and samples will be coded with a study ID.

**7. Possible Discomforts and Risks:** Colonoscopy procedures are only those performed as part of a clinically indicated procedure. Possible risks for colonoscopy biopsies include

persistent bleeding after biopsy or perforation of the wall of the colon which might require surgery. The chance of a serious complication from colonoscopy biopsy is less than 1 in 10,000.

This study will collect personal data and PHI. There is slight risk of personal information becoming public, but measures are in place to prevent that unlikely event.

**8. Possible Benefits.** There are no direct benefits of participating in this study.

**9. Conflict of Interest.** Study investigators and staff have no conflicts to report.

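### Does the n=60 power statement for gene expression need to cover the comparison by type of hypertension?

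*Combined protocol and SAP*

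**What the plan says.** Section 6, Research Plan, sets enrolment at "n=60, 30 hypertensive subjects and 30 normotensive reference subjects, equal numbers of males and females". It sets no numbers by type of hypertension.

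Under Specific Procedures, the Methods/Statistical Analyses bullets report that earlier rat experiments, comparing hypertensive with normotensive animals, "revealed significant differences between groups with a sample size of n=4 per group". The next sentence draws the conclusion: "Hence, we expect a sample size of n=60 to provide sufficient power to observe differences in gene expression". No effect size, SD, significance level, power or multiplicity rule is given. The text then turns to the organoids. There it says that no earlier data exist for a formal power calculation, and it presents 30 per group as enough to judge whether a larger study is worthwhile.

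Medical Record Abstraction says of the abstracted history: "These data will be correlated with the research results to determine any relationships or mechanisms in hypertension". It continues: "We will correlate the research results with the type of hypertension (i.e. controlled, uncontrolled, treatment-resistant".

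Two other places bear on the point. Section 4, Background, says of US adults with high blood pressure: "Approximately 20% of these people are termed treatment-resistant hypertensives because they do not achieve goal blood pressures even taking three or more antihypertensive medications". The inclusion criteria apply the "2017 ACC/AHA definition for hypertension". Both aims in section 5 compare hypertensive with normotensive reference subjects; neither mentions type.

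**The concern.** The power sentence is not limited to a named contrast, and it is the only statement of adequacy for the gene-expression data. A reader could take it to cover every gene-expression analysis in the protocol, including the one by type. That analysis can use at most 30 of the 60 subjects, and one of its three groups may hold only a handful.

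If so, a real difference of moderate size between types would probably be missed, and nothing in the text would warn a reader against taking the null result at face value. The groups also look loosely defined. Treatment-resistant subjects are by description not at goal blood pressure, so they could be counted as uncontrolled too. And if the blood pressure threshold were applied to readings at enrolment, treated patients below it would not qualify as hypertensive and the controlled group would be empty.

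**Working it through.** **The plan's own figure.** n=60 cannot be reproduced, because the protocol states no effect size, SD, significance level or power. The calculations below therefore assume one comparison at a two-sided 5% level with 80% power.

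**Expected number treatment-resistant.** Inputs: 30 hypertensive subjects (section 6) and about 20% (section 4, a national background figure used here as an assumption).

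- 0.20 × 30 = 6. The 95% range of Binomial(30, 0.2) is 2 to 11, and the chance of 3 or fewer is 12%.
- At an assumed 10%: 0.10 × 30 = 3. At an assumed 30%: 0.30 × 30 = 9.

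**Detectable difference.** For group sizes n1 and n2 and a difference of d SDs, the t statistic is noncentral t with n1 + n2 − 2 degrees of freedom and noncentrality d × √(n1·n2/(n1+n2)). Solving for 80% power:

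| Comparison | √(n1·n2/(n1+n2)) | d at 80% power | Power at d = 0.736 |
|---|---|---|---|
| 30 v 30 | √15 = 3.87 | 0.736 | 80% |
| 6 v 24 | √4.8 = 2.19 | 1.325 | 34% |

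The ratio is 1.325/0.736 = 1.8. With 3 v 27 the detectable difference is 1.77 SD, and with 9 v 21 it is 1.16 SD. Even an even split of the 30 (15 v 15) needs 1.06 SD. The loss therefore comes partly from having 30 subjects rather than 60, whatever the share in each type.

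**Against the plan's own evidence.** The 0.74 SD benchmark is only what 30 v 30 happens to detect; the protocol does not name it. The one empirical input is 4 rats per group. Suppose the rat effect was the size that 4 v 4 detects with 80% power, 2.38 SD, and that the difference between types was as large (both assumptions). Let the human SD be a multiple of the rat SD:

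| Human SD / rat SD | d in human SDs | Power, 30 v 30 | Power, 6 v 24 |
|---|---|---|---|
| 1 | 2.38 | over 99% | over 99% |
| 2 | 1.19 | 99.5% | 71% |
| 3 | 0.79 | 86% | 39% |

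The analysis by type thus runs from 39% to over 99% power over this range. The protocol does not say where in the range it falls.

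**Which claim covers which analysis.** The power sentence starts with the word Hence and follows directly from the two-group rat comparison. That is the contrast of Aim 1. The analysis by type appears only under Medical Record Abstraction, with no power statement attached.

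**The definitions.** The Background gives the feature that separates treatment-resistant subjects: above goal despite three or more drugs of different classes. Read with a list of three types, the natural rule counts them separately from other uncontrolled subjects. As to an empty controlled group, section 6 and the inclusion criteria both speak of people with a diagnosis of hypertension, and naming a controlled type shows that treated patients below the threshold are expected. The enrolment-reading interpretation is strained.

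**The case for a change.** The strongest case for a change is that the commitment to correlate with type is unconditional and carries no exploratory label, method or numbers. The protocol's cautions about lacking earlier data and needing a larger study sit in the organoid text and concern hypertensive v normotensive subjects, so they do not plainly reach this analysis. The comfort that 6 exceeds the rats' 4 is fragile: once human variability is two or three times that of the rats, 6 v 24 loses power much faster than 30 v 30. Limiting the power sentence and calling the results by type descriptive would cost only wording.

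All of that is accurate, and the weakness of the analysis stands. It shows a missing label on a secondary correlation, not a wrong figure or a conflict between sections. Almost any subgroup has less power than the full sample.

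The more substantial remedies do not gain enough. At 20%, a minimum of 10 treatment-resistant subjects means about 10/0.20 = 50 hypertensive subjects (33 to 100 at 30% to 10%), or enrichment that makes the hypertensive group less typical for the main contrast. Matching 0.74 SD without enrichment would take about 93. Nor would it help to write into the protocol that 30 v 30 has 80% power for 0.74 SD. That holds for a single 5% test. With Benjamini–Hochberg control at 5% over an assumed 15,000 independent genes, of which 1%, 5% or 10% differ by 0.74 SD, simulation at 30 v 30 lists on average 10.9 of 150, 179 of 750 and 525 of 1,500 of them. That is about 7%, 24% and 35% per gene, so the sentence would overstate what the study can find.

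**Conclusion.** The concern does not call for a change. If the 20% background figure applies, about 6 of 30 hypertensive subjects would be treatment-resistant, and a comparison of them with the other 24 could reliably find only differences about 1.8 times as large as the main contrast can. That rests on assumed test settings and on an enrolment share that the protocol does not forecast.

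The n=60 sentence makes no claim about types. It is thinly supported even for the contrast it does concern, but it is not shown to be false there. What the protocol leaves unsaid about type is the kind of gap that analysts fill sensibly: one group per subject, counts and confidence intervals for each type, and no conclusion from a null result in so few people.

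### Research biopsies are not fixed to one colon segment or to normal-appearing mucosa, and site and polyp status go unused, which adds avoidable variance to both aims

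*Combined protocol and SAP*

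**What the plan says.** The Research Plan (section 6) sets the sample at "n=60, 30 hypertensive subjects and 30 normotensive reference subjects, equal numbers of males and females". Sex is the only factor whose numbers it says will be equal.

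Under Specific Procedures, the paragraph on prepped colonoscopy biopsies says that the GI endoscopists will perform the procedures "to obtain colon biopsies", and that "All subjects will have up to 4 additional biopsies collected for research". No segment is named.

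The Recruitment paragraph of section 6 describes two sampling situations. It says "at UF, our adenoma detection rate is around 50" per cent. Of patients with polyps it says "These folks would have biopsies of other sites (polyps) already, and would get additional biopsies for study". Of the rest it says "The other 50% without polyps would only have biopsies as part of study".

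Both aims draw on the same tissue. For Aim 1, "From one part of the biopsy, the gut epithelium will be isolated" and sequenced; for Aim 2, what is left goes into organoid culture.

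Nowhere does the document require a common segment, set a normal-mucosa or polyp-distance rule, provide for recording the biopsy site, or bring site or polyp status into an analysis.

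**The concern.** Each aim compares a property of the epithelium between hypertensive and reference subjects. If one subject is sampled in one segment and the next in another, any difference between segments becomes part of the person-to-person variation against which the group difference is judged. Because the two aims share tissue, it reaches both.

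The plan's one stated device for reducing variability is to average several organoids from each individual. That lowers within-person noise. It does nothing for a difference between people that comes from where each was sampled.

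The timing also matters. Participation ends when the biopsy is done, so tissue cannot be taken again from a common site, and a location that was never written down is hard to recover. The stakes are lost precision in a study of 30 per group whose size has no formal power basis. There is also a conditional risk: if site or polyp status happened to differ between groups, part of an apparent hypertension effect would be a sampling effect.

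**Working it through.** **The plan's own figure.** The sample size cannot be reproduced. For gene expression it rests on a rat experiment with 4 per group, and for organoids the protocol says that there are no prior data for a formal calculation. No alpha, power, effect size or SD is given. What follows is therefore an illustration.

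**Inputs from the protocol.** 30 per group.

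**Assumed inputs.** One continuous endpoint; two-sample t-test; two-sided 5%; 80% power; two segments sampled equally often; a difference D between segments of 0.5 to 1 within-segment SD. None of these is in the documents.

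**1. Detectable difference as planned.** Solving the noncentral t power equation with 58 degrees of freedom gives 0.736 SD, where SD is the total between-person SD with sites mixed.

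**2. Share of variance due to site.** With two equally likely segments, the between-segment variance is D²/4 and the within-segment variance is 1, so f = (D²/4) / (1 + D²/4).
- D = 0.5: f = 0.0625 / 1.0625 = 5.9%.
- D = 1: f = 0.25 / 1.25 = 20%.

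**3. Gain from fixing the site.** The detectable difference is multiplied by √(1 − f). The equivalent group size without fixing is 30 / (1 − f).

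| D | f | Detectable difference | Equivalent n per group |
|---|---|---|---|
| 0.5 | 5.9% | 0.736 × √0.941 = 0.71 SD | 30 / 0.941 = 31.9 |
| 1.0 | 20% | 0.736 × √0.80 = 0.66 SD | 30 / 0.80 = 37.5 |

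**4. Hypothetical imbalance.** Suppose that one group has 60% of its biopsies from one segment and the other group 40%, with no true hypertension effect. The false difference is 0.2 × D. The within-group variance must include the mixing: 1 + D² × 0.6 × 0.4. The standard error is √(2 × variance / 30).
- D = 0.5: difference 0.10; variance 1.06; SE 0.266; noncentrality 0.10 / 0.266 = 0.38; type I error 6.6%.
- D = 1: difference 0.20; variance 1.24; SE 0.288; noncentrality 0.20 / 0.288 = 0.70; type I error 10.5%.

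**5. Site unrelated to group.** A gap of 20 points or more would still occur by chance in about 15.5% of 30 v 30 studies (exact binomial, probability 0.5). This is not extra error. Simulation with sites assigned at random gave false-positive rates of 4.9% (D = 0.5) and 5.1% (D = 1), so the test keeps its level.

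**The case against.** The strongest reply is that silence is not a design. The protocol leaves location unspecified; it does not say that biopsies may come from anywhere, and the endoscopists may have a consistent practice. That stands as a limit on the wording. It does not remove the point, because nothing in the protocol requires such a practice or allows it to be verified.

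A reader might infer that polyp tissue itself could enter the samples. The documents do not support that. They call polyps other sites and the research biopsies additional. What is missing is narrower: a rule on normal-appearing mucosa and separation from any polyp.

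A reader might also infer that the group comparison is biased. Nothing in the documents links segment choice or polyp status to blood-pressure group, and site chosen without regard to group leaves the type I error at its nominal level. For segment, the supported argument is precision; bias is conditional.

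A third tempting reading is that nothing can be repaired after collection. For polyp status this is wrong. The colonoscopy is a clinical procedure, and the protocol already plans to abstract medical history and relate it to the results, so polyp findings could be added later. Only an unrecorded biopsy location is hard to recover.

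Finally, the figures describe one endpoint at 5%. Aim 1 tests many genes by RNA sequencing and states no alpha, so they do not apply to it. The organoid work is meant to show whether differences merit a larger study, which lowers the priority of a modest loss of precision. Both limits stand.

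**Conclusion.** The point holds as an avoidable weakness in sampling. The protocol expects about half of its subjects to have adenomas, yet it neither standardises nor records where research tissue is taken, and it does not use polyp status. The expected cost is variance in both aims.

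At the low end of the assumed range the gain from fixing the site is small, about 2 subjects per group; at the high end it is about 8. The rise in type I error to about 7% to 10.5% depends on a 20-point imbalance that is purely hypothetical. All of these sizes rest on the assumed segment difference of 0.5 to 1 SD, two equally sampled segments and a single endpoint. The omission itself rests on no assumption. Priority is low to moderate.

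**What to change.** Amend the paragraph on prepped colonoscopy biopsies under Specific Procedures, and add matching analysis text:

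- Take all research biopsies in both groups from one colon segment chosen by the sponsor, from normal-appearing mucosa away from any polyp.
- Record the segment actually sampled for every subject.
- Abstract polyp and adenoma status from the colonoscopy record into the study database.
- In both aims, include polyp status as a covariate or run a sensitivity analysis in polyp-free subjects.

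The cost is about one protocol sentence, two data fields and one analysis statement, with no additional biopsy or visit. The downsides are that findings will apply to the chosen segment only, and that an occasional subject cannot be sampled there.
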